9.5 Auxiliary supplies

Auxiliary supplies comprise supplies other than trial products. The following auxiliary supplies will be provided by Novo Nordisk in accordance with the TMM:

- Needles for pre-filled pen (maximum length to be used is 8 mm)
- Directions for use for pre-filled pen
- Blood glucose (BG) meter
- BG auxiliaries including test strips, lancets, instructions and control solution.

Only needles provided by Novo Nordisk must be used for administration of trial product.

10 Interactive web response system

A trial-specific interactive web response system (IWRS) will be set up which can be accessed at any time via the internet or telephone. Access to the IWRS must be restricted to and controlled by authorised persons.

IWRS is used for:

- Screening
- Screening failure
- Randomisation
- Medication arrival
- Dispensing
- Treatment status
- Code break
- Drug accountability
- Data change

IWRS user manuals will be provided to each trial site.

Premature treatment discontinuation and re-initiation

If the investigator or the subject has decided to discontinue treatment, but the subject has not withdrawn consent, it is possible to re-initiate treatment, if no discontinuation criteria are met (see Section [8.1](#)). The subject will remain in the same treatment arm, and a new dose escalation period will be started, if the subject resumes treatment. The investigator must make a note and record dates of any discontinuation and re-initiation dates in the medical records and eCRF.

To register discontinuation of trial product (temporary or permanent), a 'treatment status' session is performed in the IWRS, to indicate subject should no longer receive trial product. Similarly, if the treatment should later be re-initiated, a 'treatment status' session is performed in the IWRS, to indicate subject should again receive trial product.

Withdrawal

In the case subject has withdrawn consent, a 'treatment status' session must be performed in IWRS, to indicate that subject should no longer receive trial product. If possible after confirmation by the monitor, the subject will be registered as 'withdrawal', to ensure that subject is not allowed to re-initiate trial product.

If the subject is temporarily lost to follow up during the trial, the IWRS session should not be completed until the scheduled Visit 24 at week 56 to confirm the final status.

11 Randomisation procedure and breaking of blinded codes

A randomisation session will be carried out for eligible subjects using the IWRS. The eligible subjects will be randomised centrally 1:1 to either liraglutide 3.0 mg or placebo. In addition, the subjects will be stratified between the two arms.

11.1 Breaking of blinded codes

The IWRS will notify Novo Nordisk (monitor and the Global Safety department) immediately after the code is broken.

The code for a particular subject may be broken in a medical emergency if knowing the actual treatment would influence the treatment of the subject. Whenever a code is broken, the person breaking the code must print the Code Break Confirmation Notification generated by the IWRS, record the reason, and sign and date the document.

When the code is broken, the treatment allocation will be accessible to the investigator and the Novo Nordisk Global Safety department. If IWRS is not accessible at the time of code break, the IWRS helpdesk should be contacted. Contact details are listed in [Attachment I](#).

If the code has been broken, the subject must discontinue treatment with trial product and a treatment session must be completed in IWRS.

12 Adverse events, and technical complaints and pregnancies

12.1 Definitions

12.1.1 Adverse event

An adverse event (AE) is any untoward medical occurrence in a subject administered a medicinal product, and which does not necessarily have a causal relationship with this treatment.

An AE can therefore be any unfavourable and unintended sign (including an abnormal laboratory finding), symptom or disease temporally associated with the use of a product, whether or not considered related to the product.

An AE includes:

- A clinically significant worsening of a concomitant illness.
- A CLAE: a clinical laboratory abnormality which is clinically significant, i.e., an abnormality that suggests a disease and/or organ toxicity and is of a severity that requires active management. Active management includes active treatment or further investigations, for example, change of medicine dose or more frequent follow-up due to the abnormality.

The following should **not** be reported as AEs:

- Pre-existing conditions, including those found as a result of screening or other trial procedures performed before exposure to trial product (pre-existing conditions should be reported as medical history or concomitant illness).
- Pre-planned procedures unless the condition for which the procedure was planned has worsened from the first trial-related activity after the subject has signed the informed consent.
- Non-serious hypoglycaemia is an AE, but is reported on a hypoglycaemic episode form instead of an AE form [8.4.4](#)

The following three definitions are used when assessing an AE:

- **Severity**
 - **Mild** – no or transient symptoms, no interference with the subject's daily activities.
 - **Moderate** – marked symptoms, moderate interference with the subject's daily activities.
 - **Severe** – considerable interference with the subject's daily activities; unacceptable.
- **Causality**

Relationship between an AE and the relevant trial product(s):

- **Probable** - Good reason and sufficient documentation to assume a causal relationship.
- **Possible** - A causal relationship is conceivable and cannot be dismissed.
- **Unlikely** - The event is most likely related to aetiology other than the trial product.

- **Final outcome**

- **Recovered/resolved** - The subject has fully recovered, or by medical or surgical treatment, the condition has returned to the level observed at the first trial-related activity after the subject signed the informed consent.
- **Recovering/resolving** - The condition is improving and the subject is expected to recover from the event. This term is only applicable if the subject has completed the trial or has died from another AE.
- **Recovered/resolved with sequelae** - The subject has recovered from the condition, but with lasting effect due to a disease, injury, treatment or procedure. If a sequela meets a SAE criterion, the AE must be reported as a SAE.
- **Not recovered/not resolved** - The condition of the subject has not improved and the symptoms are unchanged, or the outcome is not known.
- **Fatal** - This term is only applicable if the subject died from a condition related to the reported AE. Outcomes of other reported AEs in a subject before he/she died should be assessed as “recovered/resolved”, “recovering/resolving”, “recovered/resolved with sequelae” or “not recovered/not resolved”. An AE with fatal outcome must be reported as a SAE.
- **Unknown** - This term is only applicable if the subject is lost to follow-up.

12.1.2 Serious adverse event

A serious adverse event (SAE) is an experience that at any dose results in any of the following:

- Death.
- A life-threatening^a experience.
- In-patient hospitalisation^b or prolongation of existing hospitalisation.
- A persistent or significant disability or incapacity^c.
- A congenital anomaly or birth defect.
- Important medical events that may not result in death, be life threatening^a or require hospitalisation^b may be considered a SAE when - based on appropriate medical judgement - they may jeopardise the subject and may require medical or surgical intervention to prevent one of the outcomes listed in the definition of SAE^d.

^a. The term “life threatening” in the definition of SAE refers to an event in which the subject was at risk of death at the time of the event. It does not refer to an event which hypothetically might have caused death if it was more severe.

^b. The term “hospitalisation” is used when a subject:

- Is admitted to a hospital or in-patient, irrespective of the duration of physical stay, or
- Stays at the hospital for treatment or observation for more than 24 hours

Medical judgement must always be exercised, and when in doubt, the hospital contact should be regarded as a hospitalisation. Hospitalisations for administrative, trial-related and social purposes

do not constitute AEs and should therefore not be reported as AEs or SAEs. Hospital admissions for surgical procedures, planned before trial inclusion, are not considered AEs or SAEs.

^c A substantial disruption of a subject's ability to conduct normal life functions (e.g., following the event or clinical investigation the subject has significant, persistent or permanent change, impairment, damage or disruption in his/her body function or structure, physical activity and/or quality of life).

^d For example, intensive treatment in an emergency room or at home of allergic bronchospasm, blood dyscrasia or convulsions that does not result in hospitalisation or development of drug dependency or drug abuse.

The following adverse events must always be reported as a SAE using the important medical event criterion if no other seriousness criteria are applicable:

- suspicion of transmission of infectious agents via the trial product
- risk of liver injury defined as alanine aminotransaminase (ALT) or aspartate aminotransferase (AST) >3 x UNL and total bilirubin >2 x UNL, where no alternative aetiology exists (Hy's law).

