8.2.4 Concomitant illness and medical history

A **concomitant illness** is any illness that is present at the start of the trial (i.e. at the screening visit) or found as a result of a screening procedure or other trial procedures performed before exposure to trial product. The disease under investigation (T2DM) should not be entered as it is captured under diabetes history and diabetes complications.

Medical history is a medical event that the subject has experienced in the past. Only relevant and significant medical history as judged by the investigator should be recorded. Findings of specific medical history described below should only be entered on the specific forms.

The information collected for concomitant illness and medical history should include diagnosis, date of onset and date of resolution or continuation, as applicable.

Any change to a concomitant illness should be recorded during the trial. This also includes changes to diabetes history and diabetes complications. Any clinically significant worsening of a concomitant illness must be reported as an AE.

It must be possible to verify the subject's medical history in source documents, such as subject's medical record. If a subject is not from the investigator's own practice; the investigator must make reasonable effort to obtain a copy of subject's medical record from relevant party (e.g., primary physician). The investigator must document any attempt to obtain external medical information by noting the date(s) when information was requested and who has been contacted.

The specific medical history described below should be entered on the specific forms in the eCRF:

History of gallstone disease

Information related to gallstone disease (i.e., gallstone disease and cholecystectomy) must be recorded.

History of breast neoplasm

Information related to history of breast neoplasms must be recorded for all female subjects. Information regarding menopausal status, previous mammograms and outcome, first degree relatives with breast cancer and predisposing factors (alcohol intake above recommended local

guidelines, hormone replacement therapy, age of menarche, number of births, maternal age at first birth, and if the subject ever breastfed) should be recorded.

History of colon neoplasm

Information related to history of colon neoplasms, previous endoscopic examination(s) of the colon, history of inflammatory bowel disease, and first degree relatives with colon neoplasms must be recorded.

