8.8.2 Suspicion of acute gallstone disease

In case of suspicion of acute gallstone disease or cholelithiasis, the trial product must promptly be discontinued (no 'treatment status' session should be made in IWRS before a diagnosis of acute gallstone disease is confirmed). Appropriate treatment and careful monitoring should be initiated. Furthermore, the subject should remain in the trial (see Section [8.1](#))

The event must be reported as an AE requiring additional data collection (see Section [8.4.3.2](#) and Section [12](#)).

If acute gallstone disease is confirmed, the trial product must be permanently discontinued. However, trial product can be restarted at the investigator's discretion if cholelithiasis is ruled out or the gallbladder has been removed. Appropriate treatment and careful monitoring of the subject should be initiated. Furthermore, the subject should be encouraged to remain in the trial (see Section [8.1](#)).

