Based on a limited number of reports in the clinical development programme for liraglutide 3.0 mg, a numerical imbalance was observed for events of breast neoplasms in females and colorectal adenomas in males. There were too few cases to determine whether these cases were related to liraglutide. In addition, there are insufficient data to determine whether liraglutide has an effect on pre-existing breast neoplasia. Two positively adjudicated cases of malignant colorectal carcinoma were reported in liraglutide-treated subjects and none in placebo-treated subjects.

Allergic reactions

As in the case with all protein-based pharmaceuticals, treatment with liraglutide may evoke allergic reactions. These may include urticaria, rash, pruritus as well as anaphylactic reactions. As a precaution, subjects with known or suspected hypersensitivity to trial product(s) or related products will not be enrolled in the trial. In addition, subjects will be instructed to contact the site staff as soon as possible for further guidance if suspicion of a hypersensitivity reaction occurs

Pancreatitis

An association between the use of GLP-1RAs and pancreatitis has been suggested based on case reports received in clinical trials and during the post-marketing experience with liraglutide (in T2DM) and other GLP-1RAs. Few events of pancreatitis have been reported in clinical trials with liraglutide in weight management. After initiation of liraglutide 3.0 mg, subjects must be observed carefully for signs and symptoms of pancreatitis (see Section [8.6.5](#)). If pancreatitis is suspected, liraglutide 3.0 mg should promptly be discontinued and appropriate management should be initiated. If pancreatitis is confirmed, liraglutide 3.0 mg should not be restarted. Subjects with a history of pancreatitis are excluded from participation in the trial.

Acute gallstone disease

Cases of gallstones (cholelithiasis) and inflammation of the gallbladder (cholecystitis) were reported more commonly in adult subjects treated with liraglutide 3.0 mg compared to placebo in the clinical development programme for liraglutide 3.0 mg. From literature, it is well-known that obesity carries an increased risk of cholelithiasis and that an association between rapid and/or marked weight loss and the development of cholelithiasis is present⁴⁶. If cholelithiasis is suspected, treatment should be discontinued and gallbladder examination and appropriate clinical follow-up should be initiated.

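### Protocol 12.1.1 and 12.1.2 conflict on surgery planned before the trial when the condition has since worsened, which leaves the seriousness of a few cases open

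*Protocol*

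**What the plan says.** Protocol 12.1.1 lists what is not to be reported as an AE. One item is "Pre-planned procedures unless the condition for which the procedure was planned has worsened from the first trial-related activity" after consent, so the exemption is conditional and ends when the condition gets worse. The same section counts as an AE "A clinically significant worsening of a concomitant illness", and Section 8.2.4 repeats the duty: "Any clinically significant worsening of a concomitant illness must be reported as an AE".

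Protocol 12.1.2 defines the SAE. In-patient admission is one criterion, "or prolongation of existing hospitalisation" belongs to the same item, and note b explains what counts as hospitalisation. The note asks for medical judgement and adds that "when in doubt, the hospital contact should be regarded as a hospitalisation". It then ends with a flat exemption: "Hospital admissions for surgical procedures, planned before trial inclusion, are not considered AEs or SAEs".

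For acute gallstone disease, confirmed or suspected, Section 8.8.2 adds a separate duty: "The event must be reported as an AE requiring additional data collection". Section 8.4.3.2 sends such an event to SAE reporting if it meets the SAE criteria. None of the three protocol amendments lists a change to Section 12, so both definitions remain in force.

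**The concern.** The two sections are adjacent and a site will use both. For one set of facts (surgery arranged before the trial, condition worse since consent, patient admitted for that surgery), 12.1.1 no longer exempts the procedure, while 12.1.2 still exempts the admission from AE and SAE status. The unconditional sentence stands in the note that interprets the hospitalisation criterion, so it is the one a site is likely to consult when deciding seriousness.

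Several things follow from that decision. Under Section 12.2, an SAE needs an AE form within 24 hours and a safety information form within 5 calendar days, and SUSAR notification concerns serious reactions only. Under Section 12.3, SAEs are in general followed to a final outcome, whereas follow-up of a non-serious AE may stop at the end of the follow-up period. SAP 2.4.3.2 tabulates SAEs separately from all AEs. If two sites resolve the conflict differently, the same clinical course is serious at one and non-serious at the other.

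Gallstone disease shows why this is not purely academic. Protocol 18.1 says that gallstones and cholecystitis "were reported more commonly in adult subjects treated with liraglutide 3.0 mg compared to placebo" in the development programme. Section 8.2.4 has gallstone history recorded at entry, and Section 6.3 does not name gallstone disease as an exclusion. The example is an inference; neither of the conflicting sentences mentions gallstones.

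**Working it through.** No arithmetic applies. The plan gives no count of subjects with surgery planned before entry and no expected gallstone event rate, so the check is a comparison of texts.

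**Step 1: what each exemption covers.**

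| | 12.1.1 | 12.1.2, note b |
|---|---|---|
| What is exempted | the procedure, from AE reporting | the admission, from AE and SAE status |
| Exception if the condition worsens | yes | none |
| Date referred to | first trial-related activity after consent (start point for judging worsening) | trial inclusion (date before which surgery must have been planned), not defined there |

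The two dates do different jobs, and the undefined second one could be read as consent or as randomisation.

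**Step 2: what remains reportable whichever sentence is followed.** Note b exempts the admission. It does not exempt the worsening, which is an AE under 12.1.1 and 8.2.4 with no carve-out for planned surgery. Acute gallstone disease is in addition reported on its own event form (8.4.3.2, 8.8.2), and SAP 2.4.3.2 presents such events in tables, listings and cumulative incidence plots whatever their seriousness.

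**Step 3: the possible courses.**

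- *Planned surgery, no worsening.* Both sections exempt it. No conflict.
- *Worsening, plus an unplanned admission, a prolonged stay, a threat to life or an important medical event.* Serious under 12.1.2 on that other ground. The exemption does not matter.
- *Worsening, and the surgery is brought forward.* Whether it is still surgery planned before inclusion is doubtful. The when-in-doubt rule in note b then points to hospitalisation, and so to an SAE.
- *Worsening, and the admission takes place as arranged, with no other seriousness criterion met.* The worsening is an AE. Under 12.1.1 the procedure is no longer exempt. Under a literal reading of 12.1.2 the admission does not count, so the AE is recorded as non-serious.

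Only the last course produces a different answer, and what differs is the seriousness class.

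**Step 4: whether another passage settles it.** Sections 8.2.4 and 8.8.2 require an AE but do not set its seriousness. Section 8.4.3.2 refers back to the SAE criteria, and so to 12.1.2. Section 12.3 requires seriousness to be re-assessed when an unresolved AE worsens, again against 12.1.2. The when-in-doubt rule helps only where there is doubt, and a site that takes the flat exemption at its word has none.

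**The case against.** The strongest reply is that 12.1.1 governs whether a procedure is reported as an AE and never makes an admission serious. An SAE is an event that leads to hospitalisation, and an admission arranged before the trial that goes ahead on schedule is not clearly the result of later worsening. On this view 12.1.2 merely states the obvious, and the two sections answer different questions. Part of this stands: the documents do not say that every such case is an SAE under 12.1.1. But 12.1.2 removes AE status as well as SAE status from the admission, and 12.1.1 lifts the AE exemption in exactly this situation. On AE status, at least, the texts do not agree, and the causal question is one sites should not have to settle for themselves.

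A reader might go further in the other direction and infer that worsening gallstone disease can vanish from the safety data, or that SAEs are lost mainly from the liraglutide arm and the comparison is pulled towards no difference. The documents support neither reading. The worsening remains a mandatory AE, and acute gallstone disease is among the best-covered events in the plan. Section 18.1 describes cases reported in the development programme; it says nothing about known stones awaiting surgery. Exclusion criterion 25 also lets the investigator keep out subjects whose disorder might put their safety or compliance at risk. With no count of planned operations in either arm, neither the size nor the direction of any distortion can be stated. SAE summaries are also descriptive, with no formal test planned for them.

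**Conclusion.** The conflict is real and should be reconciled, but it is small. It affects the seriousness class of a worsening AE when the pre-planned admission is the only seriousness criterion met. It does not affect whether the AE is captured. The practical consequence is inconsistent classification between sites: some such events could fall outside expedited reporting and the SAE tables while remaining in the AE tables. The number of affected cases is unknown and may be zero. No directional bias between the arms is shown, and the primary and confirmatory analyses and the sample size are untouched.

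This rests on two assumptions: that some sites would apply note b literally, and that the amendments' own change lists are complete in leaving Section 12 alone.

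**What to change.** Amend note b of Protocol 12.1.2 so that the exemption for admissions for pre-planned surgery carries the exception already in 12.1.1: it should not apply when the condition for which surgery was planned has worsened since the first trial-related activity after the subject signed the consent form. Use that same reference date in both sections, in place of the undefined trial inclusion.

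This is one clause and one date. It needs no new data collection and no change to the SAP. The cost is possibly a few more SAE forms.

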12.1.3 Non-serious adverse event

A non-serious AE is any AE which does not fulfil the definition of a SAE.

